7.5 Participant confidentiality

All participants, delivery partner organisation representatives and activity coaches enrolled into the study will be coded with a unique study ID number. To ensure confidentiality, the final dataset will contain de-identifiable information only. All publications associated with the results of the study will involve de-identified data so participant confidentiality will be maintained. Demographic information linking the participant to the data will be stored on a separate file. Only the lead investigator will have access to this information at the conclusion of the study.

7.6 Data considerations

De-identified participant data underlying main results may be accessed by researchers who provide a methodological proposal directed to the Principal Investigator. Approval for data access will be granted

on a case-by-case basis at the discretion of the Principal Investigator. The data will be accessible from the date of this article's publication and will be available for a period of 5 years.

8. SAFETY CONSIDERATIONS

8.1 Adverse event definitions

Adverse events (AEs) are defined as “incidents in which harm resulted to a person receiving health care”. For this research study, an AE is defined as an unwanted and usually harmful outcome (e.g. fall, seizure, cardiac event). The event may or may not be related to the intervention, but it occurs while the person is participating in the intervention, i.e. while they are doing physical activity. Adverse events will be categorised as minor AEs (MAEs) or serious AEs (SAEs). A MAE is defined as an incident that occurs while the person is participating in the intervention that results in no injury or minor injury. For example, a fall where the person sustains a small cut or bruise that requires none or minor medical intervention. A SAE is defined as an incident that occurs while the person is participating in the intervention that results in death, serious injury or re-hospitalisation. Examples of SAEs are:

- Death
- Myocardial infarction
- Serious falls
- Serious fractures

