6.11 Continuation of therapy

Following the 3-month program, participants will continue to have access to the *Choose to Move* Facebook page, newsletters, and the website as they are public and readily available. If they have joined external classes, they can continue participating, however access to an activity coach will cease after the program finishes.

Participants will be followed up 6 months after the completion of the program to see if any activity they have commenced has been maintained (see Table 3). In addition, we will record any adverse events such as falls, musculoskeletal injury or cardiovascular events that has occurred post program that has reduced the ability to maintain being physically active.

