7.1 Identified risks

Participants

While the risks involved with participation in this program are extremely low, there is a slight chance that participants may experience muscle soreness if they start a new physical activity program. The Participant Information Statement (PIS) will have detailed information regarding research team contact details if any injuries or complications from the study arise. Members of the research team are experienced with assessing physical activity capabilities and advising of safety precautions, consistent with current clinical practice who will encourage participants in arranging appropriate medical treatment via their general practitioner (GP). Participants are encouraged to notify their GP before the commencement of any new exercise program (as outlined in the Get Active Form). The Choose to Move program is not an exercise program we are just educating the participants on the benefits of physical activity and encouraging participants to choose an activity they think will benefit them, so they become more active. Where appropriate, participants will be encouraged to fill in any necessary medical clearance forms required by gym/exercise classes before commencement

There is also a low risk that participants may experience emotional distress as they explore personal reasons for becoming more physically active and identify barriers/facilitators to goal setting. If this situation arises participants will be encouraged and supported by researchers and where necessary, will be encouraged to speak to their GP. Information on how to access support services (e.g., Beyond Blue, Lifeline) will be included on the PIS. The PIS will also detail that any participant has the right to not answer any question from the questionnaires or interviews if they do not wish to do so.

We also acknowledge that participation in this study requires a time cost for the participants. This has been thoroughly outlined in the PIS with the time required per study component. There is no participant costs or reimbursement for participant's time.

Delivery partner organisations/Activity coaches

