9.2 Secondary outcome(s)

The self-reported secondary outcomes will be assessed at baseline, 3- and 9-months post baseline using self-report questionnaires and will take approximately 20 minutes to complete. The Short Physical Performance Battery will be assessed at the beginning and end of the 3-month program for the face to face participants. Table 5 presents the outcome measures.

Table 5: Study outcomes and measures

Secondary effectiveness outcomes	Measure
Physical activity- participation in muscle strengthening activity	Single item question: How many days per week do you do muscle strengthening activities, such as resistance training with weights or bodyweight exercises?
Physical activity- participation in functional mobility and balance activity	Single item question: How many days per week do you do activities that emphasise balance and functional mobility training, such as yoga or Tai Chi or home exercises?
Health limitations affecting activities	Short Form 36 health survey
Ability to walk 400m	Self-reported question: Do you have any difficulty walking 400m (that is 2 to 3 blocks) outside on a level ground? (If yes, how much difficulty? Some, Much or Unable to do)
Ability to climb 1 flight of stairs	Self-reported question: Do you have any difficulty walking up 10 steps, that is about one flight, without resting? (If yes, how much difficulty? Some, Much or Unable to do)
Falls and injuries	Number of falls in past 12 months and any fall-related fractures?
Sedentary behaviour	Sedentary behaviour questionnaire
Quality of life	EuroQol EQ-5D-5L
Social Isolation	Social isolation questionnaire
Loneliness Questionnaire	Loneliness lifestyle questionnaire
Balance	Perception of balance: (“Do you feel your balance is excellent, very good, good, fair, poor”)
Fear of falling	(“Are you afraid of falling? (1 = not at all, 2 = little bit, 3 = moderately, 4 = quite a lot, 5 = extremely”)
Adverse Events (measured at follow-up 3 and 9mths only)	Experience any adverse events due to becoming more physically active? Any new or pre-existing condition have resulted in you unable to be physically active?
Short Physical Performance Battery (Face to face participants only)	The Short Physical Performance Battery (SPPB) is an objective assessment tool for evaluating lower extremity functioning.

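### Section 8.1 counts adverse events only during physical activity, which conflicts with 6.11, 8.3 and Table 5; separately, re-hospitalisation does not fit a community sample

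*Protocol*

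**What the plan says.** Section 8.1 does not require an adverse event to be caused by the program: "The event may or may not be related to the intervention". It does require a particular moment: "it occurs while the person is participating in the intervention, i.e. while they are doing physical activity". Both subcategories carry the participation condition. For minor events, "A MAE is defined as an incident that occurs while the person is participating in the intervention that results in no injury or minor injury". A serious event is one that "occurs while the person is participating in the intervention that results in death, serious injury or re-hospitalisation". The examples of serious events are death, myocardial infarction, and serious falls and fractures.

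Other sections set other scopes:
- Section 6.11 will record "any adverse events such as falls, musculoskeletal injury or cardiovascular events that has occurred post program", where the event reduced the person's ability to stay active.
- Section 8.3 has participants asked about adverse events at 3 months and at 9 months, the latter being 6 months after the program.
- Table 5 (section 9.2) has two adverse event items, asked at both follow-ups. The first is "Experience any adverse events due to becoming more physically active". The second asks whether a condition, new or old, has left the person unable to be active. A separate row asks about falls in the past 12 months and related fractures.
- Section 7.1 says that Choose to Move is education and encouragement and not exercise, and names emotional distress as one of its risks.
- Section 8.2 has staff notify the Research Manager of an adverse event within 12 hours and complete a form within 24 hours. Serious events go to the lead investigator within 48 hours.
- Section 8.4 sends serious event reporting to a University procedure and refers to a definition of serious without saying whether it is the one in 8.1.

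**The concern.** A safety definition decides which reports become forms, which are escalated, and which reach the monitoring board described in sections 6.9 and 6.12. Here the definition is narrower than the collection that surrounds it. Three entry conditions are in use: when the event happened (8.1), what the participant thinks caused it (first Table 5 item), and what it did to activity (6.11 and the second Table 5 item). The same event can qualify under one and fail another.

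The wording on seriousness is a separate defect. Re-hospitalisation presupposes an earlier admission. The entry criteria in 6.5.1 recruit people living in the community and include no index admission.

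At stake are the completeness of adverse event documentation and escalation, and the ability to classify what participants report at 9 months.

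**Working it through.** The protocol states no event rate, safety threshold or safety sample size, so there is no figure to reproduce. The check sets the definitions side by side and passes four hypothetical events through them.

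**Scopes compared**

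| Place | Condition on timing | Condition on cause | Condition on effect |
|---|---|---|---|
| 8.1 | During participation, explained as doing physical activity | None | Sorts minor from serious |
| 6.11 | After the program | None | Must have reduced ability to stay active |
| 8.3 | None beyond the 3- and 9-month surveys | None | None |
| Table 5, item 1 | None | Due to becoming more active | None |
| Table 5, item 2 | None | None | Unable to be active |

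**Four events**

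1. *A cardiac event at rest after the program, which limits activity.* Section 6.11 says to record it. Table 5 item 1 captures it only if the participant blames activity; item 2 captures it if the person became unable to be active. Under 8.1 it is not an adverse event on any reading: the person was neither in the program nor exercising. Section 8.2 then requires no form and no escalation.

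2. *A fall while exercising in month 7.* If the explanatory phrase in 8.1 governs (doing physical activity), it is an adverse event. If participating in the 3-month program governs, it is not. The text supports both readings.

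3. *Emotional distress while discussing goals with the coach.* Section 7.1 foresees this. The person is taking part in the program but is not doing physical activity, so 8.1 excludes it if the explanatory phrase governs. The difficulty arises because 8.1 equates participation with physical activity while 7.1 says the program is not exercise.

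4. *A seizure during activity, without injury, leading to a first hospital admission.* Section 8.1 gives seizure as an example of an adverse event but not of a serious one. The seriousness criterion is that the event "results in death, serious injury or re-hospitalisation". There is no death, no serious injury and no earlier admission, so read literally it is not serious. Because it caused no injury, it fits the literal wording for a minor event.

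**Direction and size.** In event 1, and on at least one reading of events 2 and 3, 8.1 removes an event from the adverse event count. In event 4 it moves an event from serious to minor. No case was found in which 8.1 adds an event that the other sections would leave out on grounds of timing. The effect on classified counts is therefore downward. Its size would need event rates by timing and cause, which the protocol does not give.

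**The case against.** The best defence is that activity-linked capture is a reasonable choice for a low-risk education program. With a single group and no comparator, unrelated background events are hard to interpret. That has force as an argument about scope, and it is a real cost of widening the definition. It does not explain why 6.11 and Table 5 then collect events outside that scope.

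It can also be said that 8.3 merely uses the defined term and so inherits the limit in 8.1. Taken alone, 8.3 is the weakest part of the conflict. But the survey items that carry it out do not apply the limit.

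On seriousness, many admissions would still qualify through serious injury or a listed example such as myocardial infarction, and the University procedure may hold a broader definition. Both points stand. What is lost is the first admission that meets no other criterion, and 8.4 does not say which definition prevails.

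Several stronger readings are tempting but unsupported:
- *That nothing after the program can count.* This holds only if program participation governs. Participants may go on exercising, and an event during that activity can meet the explanatory phrase in 8.1.
- *That the share of follow-up time outside the definition measures the harm missed.* A share of time is not a share of events. The protocol gives no rates, and the 30 minutes in the activity measure is a minimum.
- *That Table 5 asks only about events the participant attributes to activity.* The second item and the falls row carry no such condition.
- *That muscle soreness is excluded because it comes on after activity.* Section 7.1 says that "participants may experience muscle soreness if they start a new physical activity program" but not when, and the first Table 5 item would elicit it.
- *That the survey-based adverse event outcome is biased by 8.1, or that a claim of safety is thereby undermined.* That outcome is measured by the Table 5 items and not by staff applying 8.1, and none of the four hypotheses concerns safety.

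**Conclusion.** The point stands as an internal contradiction with a practical consequence. Followed as written, 8.1 leaves some events that the study itself collects outside documentation and escalation, and a literal reading leaves some first admissions outside the serious category. Classified counts are pushed downward by an amount that cannot be derived. Some excluded events will still surface in the falls row or the second survey item, but not as adverse events.

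This rests on three assumptions: that staff apply 8.1 as written; that the University procedure, which is not shown, does not override it; and that the survey forms listed in the appendices follow Table 5. How far the monitoring board's figures are affected is unknown, because its role and stopping rules are to be set elsewhere. The correction should be made before more follow-up surveys are completed, since answers to a differently worded question are hard to recover later.

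**What to change.** Reconcile 6.11, 8.1, 8.3, 8.4 and Table 5:
- State one definition of adverse and serious adverse event, and one observation window that covers the 9-month follow-up. Say in 8.4 whether 8.1 or the University procedure governs.
- Record whether the event occurred during activity, and whether it was judged related, as two separate fields and not as conditions for entry. An activity-linked summary can still be reported from them.
- Replace re-hospitalisation with hospitalisation.
- At the 3- and 9-month surveys, put a neutral question about events since the last survey ahead of the causal item.

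The cost is an ethics amendment to the protocol wording and the two follow-up surveys, and somewhat more adverse event forms. Some of these will describe unrelated events that are hard to interpret without a comparator.

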8.3 Eliciting adverse event information

Participants will be asked about the occurrence of any Adverse Events (AE) in the questionnaire completed at the 3 months (completion of program) and 9 months (6 months post completing the program) follow up.

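### Protocol section 8.1 ties an adverse event to the moment of physical activity during the intervention, which conflicts with sections 6.11, 7.1, 8.3 and Table 5 and leaves the counting rule ambiguous

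*Protocol*

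**What the plan says.** Protocol section 8.1 does not require an AE to be related to the program, but it does set a condition on timing: "it occurs while the person is participating in the intervention, i.e. while they are doing physical activity". The two severity classes carry the first half of that condition. The minor class reads: "A MAE is defined as an incident that occurs while the person is participating in the intervention that results in no injury or minor injury". The serious class sets the same timing condition and differs only in the severity of the result. The gloss that equates participation with physical activity stands only in the general AE sentence.

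Four other places bear on the same question:

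- Section 7.1 says "The Choose to Move program is not an exercise program" and describes it as education and encouragement. It names two participant risks: "there is a slight chance that participants may experience muscle soreness if they start a new physical activity program", and a low risk that "participants may experience emotional distress as they explore personal reasons for becoming more physically active".
- Section 6.11 says that after the program "we will record any adverse events such as falls, musculoskeletal injury or cardiovascular events that has occurred post program", limited to events that made it harder to stay active. It also says that coaching stops when the program ends.
- Section 8.3 asks participants about AEs at 3 months and again at the "9 months (6 months post completing the program) follow up".
- Table 5 (section 9.2) lists AEs at 3 and 9 months as a secondary outcome. One item asks about events caused by becoming more active. The other asks about new or existing conditions that prevented activity.

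**The concern.** A definition of an adverse event has to tell staff which events to count and which to leave out. Section 8.1 does so by timing, and its timing clause does not match what the program is or when the protocol collects events. The clause treats the intervention and physical activity as the same thing. The delivered program is coaching and group education, and participants are physically active mostly in their own time.

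Two uses of the definition are exposed. First, AEs at follow-up are a listed secondary outcome, and their count would depend on which rule a classifier applies. Second, section 8.2 starts its clocks (12 hours to notify the research manager, 24 hours to complete the AE form) when an AE becomes known. An event that fails the timing clause starts neither clock, even if it is a kind of harm that the protocol foresees.

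**Working it through.** The protocol gives no figure to reproduce, so the check sets its passages side by side.

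**Step 1: what the clause can mean.** The program lasts 3 months (sections 6.5.2 and 6.5.3). Scheduled contact is 8 group meetings of 1 hour and one 30-minute consultation: 8 × 1 + 0.5 = 8.5 hours. Section 7.1 calls this education, not exercise. The clause in section 8.1 can then be read in two ways:

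- Reading A, program period: the event happens during the 3-month program, and the gloss is set aside.
- Reading B, gloss governs: the event happens while the person is physically active, whenever that is.

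Taken literally, the sentence asks for both at once, which is narrower than either.

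**Step 2: apply the rules to typical events.**

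| Event | Reading A | Reading B | Collected elsewhere in the protocol |
|---|---|---|---|
| Emotional distress during goal setting | In | Out | Not clearly an event caused by becoming more active (Table 5) |
| Fall while arriving at a group meeting | Arguable | Out | Table 5 falls item |
| Fall on a walk alone, month 2 | In | In | Table 5 falls item; causal item if attributed to new activity |
| Cardiac event some hours after new activity, month 2 | In | Out | Table 5 causal item, if attributed |
| Fall in an exercise class, month 6 | Out | In | Section 6.11, if it reduced activity; Table 5 |
| Fall at home, not during activity, month 6 | Out | Out | Section 6.11, if it reduced activity; Table 5 falls item |

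Only the month-2 walk is counted under both readings. Under the literal sentence (A and B together) it is the only one of the six that is clearly an AE.

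**Step 3: the risks in section 7.1.** Emotional distress comes from reflecting on motives and barriers, not from moving. It fails the AE sentence with its gloss. It could come in only if the MAE sentence, which lacks the gloss, were read on its own, but MAEs are a category of AE. Muscle soreness is different. Section 7.1 links it to starting new activity and does not say when it appears. Soreness that begins during activity fits section 8.1; soreness that appears later does not.

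**Step 4: the follow-up period.** From baseline to the last AE questionnaire is 9 months, and the program takes 3. The post-program part is 9 − 3 = 6 months, or 6/9 = 67% of follow-up. That share is outside section 8.1 on Reading A only. On Reading B, events during activity in those months are inside and all others are outside.

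**Step 5: the causal test.** Table 5's first AE item requires a cause and sets no limit to the moment of activity. Section 8.1 requires the moment and no cause. An unrelated faint during a walk passes section 8.1 and fails the Table 5 item. A strain that emerges the day after new exercise does the reverse.

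**The case against.** The strongest defence is that harms are collected whatever section 8.1 says. Table 5 asks about events caused by becoming more active, about conditions that prevented activity, and about falls and fall-related fractures. Section 6.11 adds post-program falls, musculoskeletal injury and cardiovascular events. The study is an uncontrolled, low-risk education program, so unrelated events have no comparator and a narrow definition is defensible in principle. This stands in part. It shows that the data would not be empty. It does not say which of those records are AEs for the outcome or for section 8.2.

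A reader might infer more than the protocol supports, in four ways:

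- That both risks in section 7.1 are shut out. Only emotional distress clearly is; the timing of soreness is not stated.
- That every post-program event is shut out. This needs the program-period reading. If the gloss governs, a fall in an external class in months 3 to 9 would count.
- That the harm count must come out near zero. The Table 5 items and section 6.11 speak against this.
- That SAE reporting and the stopping rules rest on section 8.1. Section 8.4 sends SAE reporting to the University's procedure and refers to an SAE definition that may be the procedure's own and is not shown. Section 6.12 leaves the monitoring board's rules to be set in advance and does not tie them to section 8.1.

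**Conclusion.** The concern holds as a conflict within the protocol that should be fixed. Section 8.1 equates the intervention with physical activity, contrary to section 7.1. As written it leaves out emotional distress and any harm that appears outside activity. Read with the 3-month program, it also leaves out the events of the last 6 of 9 months that sections 6.11 and 8.3 set out to collect; on the other reading it keeps only those that occur during activity. With the causal item in Table 5, the AE outcome has inclusion rules that disagree, and the section 8.2 notification steps depend on whichever rule a staff member applies.

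The number of events affected cannot be stated, because the protocol gives no expected event rates. The conclusion rests on the plain wording and on treating MAEs and SAEs as categories of AE, as section 8.1 presents them. It does not rest on any assumption about when soreness appears or about what the University's SAE procedure says.

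**What to change.** Replace the timing clause in section 8.1 with one window that has a stated start (consent, for example) and runs to the 9-month follow-up. It should not be limited to the moment of physical activity, and it should be the same for AE, MAE and SAE.

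Record on the AE form the circumstance of the event (during activity, after activity, group meeting, consultation, physical performance test, other) and its judged relatedness. Activity-related events can then still be reported separately.

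Reconcile section 6.11, section 8.3, the AE items in Table 5 and the SAE definition referred to in section 8.4 with this one definition. Aligning only the first two would leave the causal item and the SAE definition out of step.

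The cost is protocol wording submitted as an amendment, fields on one form, and more unrelated events to log in 160 people.

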8.2 Assessment and documentation of adverse events

The Research Manager will be notified within 12 hours of any staff member witnessing or becoming aware of a participant reporting an AE. The research staff member will complete an AE data form within 24 hours of knowing about the AE. If a SAE occurs, the Research Manager will notify the lead investigator within 48 hours.

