8.4 Adverse event reporting for serious or significant adverse events

Reporting of SAEs will follow The University of Sydney standard operating procedure on clinical trial safety reporting, using the SAE definition and procedures.

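### The two adverse event classes in section 8.1 do not fit its own examples or cover every event, so some events can miss the serious-event route

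*Protocol*

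**What the plan says.** Section 8.1 of the Protocol first says what counts as an adverse event: "an AE is defined as an unwanted and usually harmful outcome (e.g. fall, seizure, cardiac event". It then allows two classes and no third: "Adverse events will be categorised as minor AEs (MAEs) or serious AEs (SAEs".

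- **Minor:** an incident when the person is "participating in the intervention that results in no injury or minor injury". The illustration is a fall with a small cut or bruise that needs little or no medical attention.
- **Serious:** an incident when the person is "participating in the intervention that results in death, serious injury or re-hospitalisation". Four examples follow, one of which is "Myocardial infarction", listed with no condition about injury.

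The class then decides part of the route. Section 8.2 applies one step to every event: "The Research Manager will be notified within 12 hours of any staff member witnessing or becoming aware of a participant reporting an AE". An adverse event form follows within 24 hours. A further step is for serious events only: "If a SAE occurs, the Research Manager will notify the lead investigator within 48 hours". Section 8.4 sends serious events through the University's standard operating procedure, "using the SAE definition and procedures". Sections 6.9 and 6.12 set up an independent DSMB whose remit is adverse events generally.

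**The concern.** The definition of an adverse event takes in medical events that are not injuries. The minor class is then defined by the degree of injury and nothing else. A definition of this kind has to do two things: place each of its own model events sensibly, and leave no event without a class. Section 8.1 does neither reliably.

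This matters because the class carries a consequence. Only a serious event is passed to the lead investigator within 48 hours and enters the reporting procedure of section 8.4. If the wording lets a medical event be filed as minor, or leaves the person completing the form to choose between two classes that do not fit, that escalation depends on individual judgement. The study encourages inactive adults aged 50 and over to become more active, and it names seizure and cardiac event itself, so these are events the sponsor has foreseen.

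**Working it through.** No arithmetic applies, and the Protocol states no figure on this point to reproduce. The check applies the section 8.1 wording to each type of event and follows the result through 8.2 and 8.4. In every case the event is taken to occur during participation, as 8.1 requires.

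| Type of event | Minor wording | Serious criteria | Result |
|---|---|---|---|
| Fall with a bruise | Met | Not met | Minor, as intended |
| Seizure, or cardiac event other than myocardial infarction; no injury, no death, no hospital stay | Met | Not met | Minor; no 48-hour notice |
| The same, ending in death or re-hospitalisation | Not excluded by its words | Met | Serious, whatever the injury |
| The same, leading to a first admission, no injury | Met | Not literally met | Unclear |
| Non-fatal first myocardial infarction with a first admission | Not excluded by its words | Not clearly met | Serious by the example list only |
| Injury more than minor but less than serious, no re-hospitalisation | Not met | Not met | Neither class |

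Three faults follow.

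1. **The minor criterion does not suit the model events.** Two of the three examples in the definition, seizure and cardiac event, need not involve an injury. The only test for the minor class is injury, so these events meet it by default unless a serious criterion intervenes.
2. **The serious criteria do not line up with the sample or with their own examples.** Section 6.5.1 recruits adults living in the community, and nothing there requires a recent hospital stay. Taken literally, re-hospitalisation does not describe a first admission. Myocardial infarction is named as serious, yet a non-fatal first event is neither a death nor a re-hospitalisation in the literal sense, and it is not obviously an injury.
3. **The classes leave a gap.** Between a small cut or bruise and a serious injury there is a middle range, and no class is provided for it. The examples of serious falls and serious fractures do not close the gap, because the word serious is not defined beyond the criteria and examples already listed.

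Section 8.4 can be read in two ways. If the definition it means is that of 8.1, all three faults carry through. If it means the University procedure's own definition, two definitions operate at once. Section 8.4 also governs only the reporting of serious events, so an event already filed as minor under 8.1 may never be tested against the second definition.

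As to the consequence, the step to the Research Manager within 12 hours and the form within 24 hours apply to every event. The 48-hour notice and the 8.4 route apply to serious events only. Those two steps are what a misclassified event loses.

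**The case against.** The best defence is that injury in 8.1 means bodily harm rather than a wound. The section opens by describing adverse events in terms of harm, and its serious list includes a non-traumatic cardiac event, so serious medical events were plainly meant to be serious. The minor illustration also refers to minimal medical intervention, so an event needing more than that does not plainly belong in the minor class. The University procedure may already capture the events in question. The Protocol describes the program as educational, with very low risk.

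Much of this is fair about intent. It does not repair the text. The reference to medical intervention belongs to an example, not to the criterion. A broad reading of injury still leaves the middle range without a class and first admissions unaddressed. The procedure is not among the documents, so it cannot be relied on in either direction. Low risk bears on how often the fault would show, not on whether the wording works.

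A reader might go further, and the documents do not support these stronger readings:

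- **That seriousness is graded by injury alone, so that every seizure or cardiac event without injury stays out of the serious route.** Death and re-hospitalisation qualify without injury, and myocardial infarction is escalated by name.
- **That minor events go no further than the Research Manager.** Every event is documented, and the DSMB monitors adverse events as a whole.
- **That the DSMB would see wrong minor and serious counts.** Nothing says that it receives such counts.
- **That the cardiovascular events mentioned in section 6.11 would be filed as minor.** That section concerns recording events after the program and sets no grading.
- **That a stated share of events is misgraded.** The types in the table are illustrations chosen to test the wording, not a frequency.

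**Conclusion.** The point holds in limited form. Section 8.1 fixes a two-class rule that does not fit its own examples and is not exhaustive, and 8.4 leaves open which serious-event definition governs. Followed as written, the rule can class a non-injury medical event as minor, leaves a first admission unclear, and gives no class to an injury between minor and serious.

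The effect is confined to the 48-hour notice to the lead investigator, the section 8.4 reporting route, and the consistency of the minor and serious labels. No number of affected events can be given, because the documents contain no event rates. The effectiveness analysis is not affected. The amendment is still worth making because it concerns safety reporting and is cheap.

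The conclusion rests on reading the criteria as worded and makes no assumption about what the University procedure contains. If that procedure's definition is broader and is in fact applied to every event at first classification, the practical harm shrinks. The inconsistency within 8.1 would remain.

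**What to change.** Amend section 8.1 and align it with section 8.4:

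- Reconcile the adverse event examples, the minor and serious criteria, and the serious examples in 8.1 with the definition meant in 8.4, so that one seriousness definition applies throughout. The sponsor should take its content from its own procedure; none is proposed here.
- Make sure that definition does not depend on injury alone and says explicitly how a first hospital admission is treated.
- Define a minor adverse event as every adverse event that does not meet the seriousness definition, so that no event is left without a class.
- State in 8.4 that its definition and that of 8.1 are the same, and carry the wording into the adverse event form.

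The cost is a wording amendment with HREC review under section 6.8, a revised form, and possibly a few more serious event reports.
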